Study patients will be randomized into groups 1, 2, or 3 immediately AFTER initial thorough wound cleansing/debriding by the nurse or physician. Randomization will be accomplished using an electronic random number generator (an app).

After a member of the UHWI surgical team performs the initial cleansing/debriding, the control group (1) will have their ulcer dressed as usually done at UHWI. Wounds are dressed with saline-soaked gauze, covered with dry gauze. One wrap of stretch gauze will hold the dressing in place. Patients will clean the wound by vigorously wiping with gauze soaked in homemade normal saline (1 tsp salt/500ml water bottle), center to edges, at each dressing change, unless already very clean. Clean wounds will simply be irrigated with normal saline at each dressing change. Patients experienced with using papaya for debridement of their ulcers may apply it only to the open wound, avoiding contact with the periwound, to remove slough or eschar. If patients observe green exudate, they are permitted to add one teaspoon of vinegar to their bottle of saline. Dressings in group (1) will be changed daily. The dressings will be soaked off if they become adherent.

After initial cleansing/debriding, patients in the improvised dressing group (2) will then have a thin layer zinc oxide paste applied to the dried periwound, carefully avoiding the open wound.⁹⁷ A piece of a clean new plastic bag (food-grade World Star 1 mil LD bags, or the equivalent, purchased from the Papine Market across John Golding Road from the University of the West Indies), cut slightly larger than the ulcer will be gently conformed to the moist wound contours and sealed onto the zinc oxide paste. The bag will be fenestrated with a small slit using a number 11 scalpel or clean scissors prior to placing it on the ulcer in order to allow excess fluid to escape. The edges of the slit will be approximated. Clean gauze will be placed lightly over the slit to capture escaping fluid. One wrap of stretch gauze will hold the dressing in place. Patients will be instructed to change the dressings daily, irrigating with normal saline at each dressing change.⁶

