After initial cleansing/debriding, the advanced dressing group (3) will have a cut piece of a 4"x24" standard (pink) PMD roll large enough to extend at least 0.5 cm beyond all open and closed (inflamed or damaged) wound edges applied as per the Instructions for Use (the periwound is blotted dry, but the wound bed remains moist from the final saline rinse). One wrap of stretch gauze will hold the PMD dressing in place. The approximate open wound edges will be marked on the dressing backing. As per the manufacturer's instructions for use, patients will change the dressings when saturation reaches any of the wound edges, as indicated by a change in color on the backing of the dressing, visible through the stretch gauze. Routine rinsing will not be performed; the wounds will be rinsed at dressing changes only if visible loose debris is present.

All study patients will receive education about their illness and pain medication prescriptions per usual protocol. Patients are advised to use a compression wrap whenever their foot is dependent, as often as they are able to tolerate it. They will each be given a zipper-bag to contain and keep their wound management supplies clean.

Patients will be required to come to the UHWI surgical clinic dressing area in person weekly during the initial 4 weeks of study enrollment so that wound photos can be taken and the data for the ten dependent variables that are to be assessed weekly can be obtained. If their SCLU is clean without evidence of complications, patients/families who demonstrate the ability to take adequate pictures of their study SCLU with their mobile devices may instead send photos of their wound and their data collection sheets to the research team via end-to-end encrypted text messaging system (WhatsApp). All patients must agree to come to UHWI at least once per month to avoid being withdrawn from the study. Appointment times will include evenings and Saturdays to accommodate the schedules of students and employed patients.

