As a token of appreciation from the research team and an incentive for patients to return for their study clinic visits, each participant will be presented with a 500JM phone card at the end of each of the three 4-week study periods.

All wound management supplies for all three groups will be donated. Shipping and handling fees will be paid by the Principal Investigator with funds from a Wound Healing Foundation grant. Tallies of supplies used at dressing changes will be priced using the cost of medical supplies purchased by the SCU to determine the estimated cost of the treatment supplies for each patient. The PMD rolls will be valued at \$26.99US.⁹⁸

The Principal Investigator will de-identify the data and compile it from the patient Data Collection Tools onto an Excel spreadsheet. This spreadsheet and the de-identified wound photographs will be backed up onto the Principal Investigator's second password protected hard drive via a secure internet connection at least weekly. Two encrypted USB drives containing the data, including wound photographs, will be updated weekly on an alternating schedule and stored in a securely locked file in [name] office in UWI Department of Surgery.

i. Statistical analysis

A consultant, [name], PhD, Senior Biostatistician at The University of Texas Medical Branch in Galveston, will undertake the analysis.

When all of the patients have completed the study, the remainder of the data from the deidentified Data Collection Tools will be transcribed into an Excel spreadsheet by the Principal Investigator. The data will then be evaluated by the biostatistician using the most recent version of SPSS. Groups will be compared with respect to each of the 14 dependent variables, taking into account any confounding from the 11 independent variables. Results will be reported using descriptive statistics (means, modes, medians, frequencies), student's t test, and ANOVA with 95% CIs, using intent-to-treat.¹³ If the improvised dressing does not attain statistical superiority to usual practice, 80% CIs will be calculated with drop-outs removed from the analyses to evaluate noninferiority.^{13, Appendix: From Oczkowski SJW} Complications will be evaluated both individually and collectively by collapsing the pertinent columns.

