Research questions (1) and (2) will be addressed by using analyses of covariance (ANCOVA) to determine if patients in the improvised dressing group (Group 2) had superior results (95% CI's will fall within *f*, the superiority margins) from usual practice (Group 1) or advanced dressings (Group 3), or, if this is not demonstrated, failed to vary significantly (80% CI's will fall within *f*, the inferiority margins) from usual practice (group 1) or advanced dressings (group 3) with respect to each of the dependent variables, controlling for relevant patient characteristics (the independent variables).

Research question (3) will be addressed with descriptive statistics across Likert items regarding endorsement of and concerns with use of the improvised dressing clinically or in future studies. Qualitative comments will be summarized across providers into content themes. Any differences between nurses, patients, family members, and physicians will also be explored and noted.

All health care providers at UHWI participating in the study will be surveyed to explore their concerns as well as their opinions about each dressing choice, using both qualitative open-ended and a quantitative question on a Likert scale. Results will then be shared with the participating clinical staff to provide them with the evidence concerning each of the three dressing protocols.

j. Data handling and record keeping

All study data will be transferred from written documents to the Principal Investigator's password protected electronic devices, de-identified, and then transmitted over secure internet connections to the backup hard drive in the USA. The paper study documentation and the two encrypted USB drives containing the raw data will be stored in a securely locked file in in [name] office in UWI Department of Surgery for a period of at least two years after the study has been published, after which they may be destroyed.

When all of the patients have completed the study, members of the UHWI research team will proofread the Excel spreadsheet with the de-identified data for transcription errors. This data will then be evaluated by the biostatistician using the most recent version of SPSS.

4. Ethical Considerations

This study will be approved by the Ethics Review Committee (ERC) at UWI and the Jamaican Ministry of Health (MOH) prior to its implementation. It will be listed on clinicaltrials.gov prior to the recruitment of the first study patient.

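### Section 3i plans only equal-variance methods, although materials cost is likely to vary more in group 3: name arm-specific variances for cost and dressing-change time

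*Combined protocol and SAP*

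**What the plan says.** Section 3i (Statistical analysis) compares the groups on all 14 dependent variables, with results reported by "student's t test, and ANOVA with 95% CIs, using intent-to-treat". It then says that questions 1 and 2 will be answered "using analyses of covariance (ANCOVA) to determine if patients in the improvised dressing group (Group 2) had superior results" over group 1 or group 3, controlling for the baseline variables. If superiority is not shown, "80% CIs will be calculated with drop-outs removed from the analyses to evaluate noninferiority". No unequal-variance test, robust standard error or check of variances is named.

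Two of the variables listed in section 3d are materials cost (variable 7) and time spent on dressing changes (variable 8). Both are components of research question 2 in section 2.

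Section 3h sets how often dressings are changed:
- Group 1: "Dressings in group (1) will be changed daily".
- Group 2: "Patients will be instructed to change the dressings daily".
- Group 3: "patients will change the dressings when saturation reaches any of the wound edges". The piece is cut from a 4 x 24 inch roll to extend beyond the wound edges, and the roll is valued at US$26.99.

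The documents give no SD for cost or time in any arm.

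**The concern.** An ordinary ANOVA or ANCOVA fitted to three arms estimates one residual variance and uses it for every contrast. Group 3's spread then enters the interval for group 2 v 1, although group 3 is not part of that comparison.

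For materials cost there is a reason in the design to expect unequal spread. In group 3, cost is piece size times price times a number of changes that differs between patients. In group 2 it is mainly a small piece of inexpensive plastic, with light gauze, at an instructed daily frequency.

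If group 3 is the most variable arm, the 2 v 1 interval is too wide and a real saving against usual practice can be missed. The 2 v 3 interval is too narrow and overstates certainty.

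**Working it through.** **Inputs from the documents.** Section 3f gives about 30 per group, 90 in all, and a 25% dropout allowance. The plan's recruitment figure reproduces: 90 / (1 − 0.25) = 120. The 30 per group rests on earlier sample sizes and the Central Limit Theorem, with no SD or power behind it, so it is taken as given. The roll is 10.16 × 60.96 cm = 619 cm², so 26.99 / 619 = US$0.044 per cm².

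**Three-arm pooled variance.** Let groups 1 and 2 have SD s and group 3 have SD r·s. The value of r is an assumption. With equal arms the pooled variance is s²(2 + r²)/3. The ratio of model SE to true SE is then
- 2 v 1: √((2 + r²)/3)
- 2 v 3: √(2(2 + r²) / (3(1 + r²)))

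At r = 2 these are √(6/3) = 1.41 and √(12/15) = 0.89. At r = 3 they are √(11/3) = 1.91 and √(22/30) = 0.86.

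Simulated coverage of 95% intervals (normal data, 30 per arm, 200,000 trials per setting):

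| r | SE ratio 2 v 1 | Coverage 2 v 1 | SE ratio 2 v 3 | Coverage 2 v 3 |
|---|---|---|---|---|
| 0.5 | 0.87 | 91.1% | 1.10 | 96.7% |
| 1.5 | 1.19 | 98.0% | 0.93 | 93.3% |
| 2 | 1.41 | 99.3% | 0.89 | 92.0% |
| 3 | 1.91 | 99.96% | 0.86 | 90.4% |
| 5 | 3.00 | 100% | 0.83 | 89.3% |

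For the planned 80% intervals at r = 2, coverage is 92.7% (2 v 1) and 74.8% (2 v 3).

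**Power for 2 v 1.** A contrast with 90% power under its own SE lies 1.96 + 1.28 = 3.24 SEs from zero. With the SE inflated 1.41 times, the critical value is 1.96 × 1.41 = 2.77 true SEs, and power is Φ(3.24 − 2.77) = Φ(0.47) = 68%. At r = 3 it is Φ(3.24 − 3.75) = Φ(−0.51), about 30%.

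**Two-sample Student's t.** Group 3 does not enter 2 v 1, so coverage is 95.0%. For 2 v 3 with 30 v 30, the pooled and unequal-variance SEs are identical, and coverage is 94.9%, 94.7% and 94.6% at r = 2, 3 and 5. It fails when arm sizes differ: at r = 3, 36 in group 2 and 24 in group 3 gives 90.1%, and 24 and 36 gives 97.7%. Sections 3f and 3h describe a random number generator and state no blocking, so unequal arms are possible. Averaged over simple randomisation of 90 patients, coverage at r = 3 is 94.3%.

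**How large r might be for cost.** With assumed median wound size 5–20 cm², 2–4 group 3 changes a week and near-constant cost in group 2, group 3's SD is far above group 2's. Against group 1 the answer depends on the gauze price, which is not stated. The SD ratio of group 3 to group 1 is about 7.5–21 at US$0.002 per cm², 1.5–4.2 at 0.01, and 0.5–1.4 at 0.03.

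**How large r might be for time.** Take weekly time as changes × minutes, independent, with equal mean minutes in every arm. A daily arm has SD 7m·c, where m is mean minutes and c their CV. Group 3, with k changes on average and CV of count v, has SD k·m·√((1 + v²)(1 + c²) − 1). With c = 0.4, k = 3 and v = 0.3, the ratio is 3 × 0.514 / 2.8 = 0.55. With v = 1.0 it is 3 × 1.149 / 2.8 = 1.23. Over 2–5 changes a week and c from 0.2 to 0.6, it runs from 0.33 to 3.7.

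**After the change.** Welch intervals cover 94.9–95.1% (95% level) and 79.9–80.2% (80% level) in every setting tried, for both contrasts, at r from 0.5 to 5 and with equal or unequal arms.

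**The case against.** A reader might infer that every method in section 3i gives errors in opposite directions for the two contrasts. The documents do not support that. Only a three-arm residual variance does so, and section 3i does not say that the ANCOVA is one three-arm model. Two-sample Student's t with equal arms stays near 95% for both.

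A reader might also infer that the protocol makes group 3 far more variable on both cost and time. For time it does not. Section 2 expects fewer changes in group 3, and section 3h drops routine rinsing there. Group 1 carries the steps that differ between patients: wiping unless the wound is clean, optional papaya, and soaking off. If time is recorded per change, which section 3d leaves open, frequency does not enter at all.

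For cost, section 1b calls usual practice and the advanced dressing both relatively expensive. Group 2's plastic is also cut to ulcer size, initial area is a planned covariate, and daily changing is an instruction while cost comes from supplies actually used. The excess over group 1 is therefore likely only if gauze is cheap.

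It would also be tempting to quote a much larger undercoverage. A simulation of 12-week cost with assumed prices and ulcer sizes, adjusted for initial area, gave SDs of $23, $12 and $49 and 85% coverage for 2 v 3. From those SDs alone, the SE ratio is √[((23² + 12² + 49²)/3) / ((12² + 49²)/2)] = √(1024.7/1272.5) = 0.90, or about 92% coverage. The remainder is probably skewed cost, a different problem.

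These objections limit the size and reach of the point. What stands is that no method robust to unequal variances is named, where unequal variance is likely for cost.

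**Conclusion.** The point holds in a limited form. Section 3i names only equal-variance methods, and the design makes unequal variance likely for materials cost, at least between groups 2 and 3. If one three-arm residual variance is used, both contrasts are miscalibrated. At an assumed 1:1:2 ratio the 2 v 1 SE is 1.4 times too large and 2 v 3 coverage is about 92%. At 1:1:3 the figures are 1.9 times and about 90–91%. With equal arms this mechanism alone cannot take 2 v 3 coverage below about 89%. The direction for 2 v 1 is not fixed, because it depends on a gauze price the documents do not give, and the direction for time is undetermined.

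Severity is minor. The point touches two of 14 dependent variables, both secondary components of question 2. It is not shown for ulcer area, which section 3c uses for question 1. Question 2 as posed in section 2 compares only with usual practice. If group 3 is the more variable arm, the error in that contrast is lost power rather than false certainty. The ratios are illustrations, not estimates from the plan.

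**What to change.** Add one sentence to section 3i: for materials cost and dressing-change time, between-group contrasts use arm-specific variances, by Welch's t and Welch ANOVA, and by ANCOVA with heteroscedasticity-consistent (HC3) standard errors. An acceptable equivalent is to estimate each contrast from its two arms only, with unequal variances. State in section 3d whether variable 8 is per change or per week.

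This works whichever arm turns out to be more variable. It costs a sentence and a software option, does not change the sample size, and loses a few degrees of freedom if the variances are in fact equal. It does not cure skewed cost: in the assumed cost simulations, HC3 intervals covered 95–97% for 2 v 1 but 87–96% for 2 v 3.

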Although non-inferiority is an acceptable outcome for the improvised dressing, the review of the literature supports the expectation that it will outperform usual practice. This superiority study design eliminate the motive for the blinded evaluators to minimize differences between groups, biasing the results.¹³ If superiority is attained, the results will be evaluated with intent to treat (ITT) analysis.

If superiority is not demonstrated, the data for the improvised dressing and usual practice dressing will be re-evaluated to assess for noninferiority.¹³ Contrary to superiority trials where use of intention-to-treat is employed to protect against type 1 error, the appropriate approach for noninferiority trials is to use a per-protocol approach,¹³ which, at worst, would exaggerate the differences between treatment groups, thereby yielding a more conservative estimate in the setting of a noninferiority trial.¹³ Thus, only those patients completing treatment in the group to which they were randomized will be retained for any non-inferiority analyses (see appendix for further details).

b. Study population

Individuals diagnosed with sickle cell disease who have a SCLU and reside in the parishes of St. Catherine, St. Andrew, or Kingston parishes of Jamaica and respond to advertisements, recruitment phone calls, or flyers posted at the Sickle Cell Unit (SCU) clinic and UHWI prior to and during the enrollment period will be invited to participate in the study. Members of the UHWI surgical team will call all patients identified by the SCU as having had a SCLU within the past two years to invite them to participate in the study. Jamaican residents who otherwise qualify but who live outside the study area will be included only if they agree to provide their own transportation and faithfully attend all clinic visits.

c. Sample

Study participants must have HbSS or HbS β^0 sickle cell disease, be between the ages of 13 and 70, and have a chronic SCLU, defined as a wound in a patient with sickle cell disease that has been open for at least one month and is below the knee, excluding the plantar surface of the foot. All SCLUs on a single patient will be dressed with the same dressing protocol. The largest ulcer at initial presentation is the study SCLU. If two or more SCLUs in close proximity join into

an enlarged ulcer during the first four weeks of the study, the sum of the initial areas will be considered the initial wound size for calculation purposes.

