- Based upon previous studies and the Central Limit Theorem, an estimated 90 participants (~30 per group) may be required for the differences between groups to reach statistical significance.^{12,23,88,89,96} Up to 120 patients will be recruited to allow for a 25% dropout rate. Based upon the literature review, pain, costs, wound size, and quality of life are expected to be significantly improved using the improvised dressings. However, because SCLUs are, historically, very slow to heal and often enlarge, complete wound closure is not an expected outcome for all patients.

g. Procedures for recruitment and consent

The study will be advertised using free community information channels such as church bulletins and radio outlets. Social media sites such as the CAIHR Facebook page will also be employed. Qualifying patients in the SCU database from up to two years prior to the study initiation will be called by the UHWI surgical team, alerting them to the dates for registering to participate. Flyers will be posted at the SCU in advance. Consent will be obtained by a member of the research team while the potential participant is waiting to be seen for wound care.

h. Data collection

The site for this study is the surgical clinic dressing area at the University Hospital of the West Indies (UHWI), Mona, Jamaica. The adjacent Sickle Cell Unit (SCU) will refer any SCLU patients to UHWI during the study period. UHWI is consistently well staffed with competent Jamaican health professionals. The UHWI surgical team will lead the study. Relatively few Jamaicans live or work in air-conditioned environments, ^[data in appendices] allowing the results from this out-patient population to translate to less developed tropical countries.

To ensure consistency, members of the research team will practice until they can demonstrate competency with all three dressing change procedures and with explaining the study forms prior to study patient recruitment.

Enrollment in the study will begin within two weeks of the day the Principal Investigator arrives at the Mona campus and will close 60 days later, or when a maximum of 120 patients have enrolled. All sickle cell positive patients presenting to UHWI with lower leg ulcers during the enrollment period will be screened for eligibility to enter the study. Each patient's data will be recorded for a total of 12 weeks, or until their SCLU has been closed for 2 weeks, whichever comes first.

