Weekly, de-identified photographs will be sent by the Principal Investigator to be viewed by two blinded wound experts ([name] and [name]) off site. If the blinded experts, or anyone else involved in the study, expresses concern that a patient is exhibiting signs of possible infection, maceration that is delaying healing, or wound deterioration, a physician at UHWI or the SCU who is not otherwise involved in the study will be asked to evaluate that patient. The patient's dressings will be removed prior to this evaluation so that their treatment group will not be revealed to the physician (the evaluation by the physician is thus blinded to treatment group). If the physician determines that the patient's condition has not improved with the prescribed treatments (e.g., antibiotics), the patient will be withdrawn from the study. Any

patient who transitions out of the group to which they were randomized for any reason will receive usual treatment for their ulcer for the remainder of their 12 week study period.

When the treatment personnel at UHWI or the blinded remote observers state that the patient's wound appears to be closed, a physician at UHWI or the SCU who is not otherwise involved in the study will be asked to evaluate that patient. The patient's dressings will be removed prior to this evaluation so that their treatment group will not be revealed to the physician. Wound closure is defined as 100% epithelialized with no discernible scab or exudate production (a paper napkin blotting the area remains dry). Patients will be reassessed two weeks later to verify that the wound was truly closed and did not immediately recur.

Patients who are diagnosed with wound closure or have completed the 12 week study period will be taken aside privately and asked to rate the acceptability of their treatment using a 5 point Likert Scale. A family decision-maker will also be privately asked to rate the acceptability of the treatment. One of the research team members will enter this basic acceptability data for the patient and the family on the patient's Data Collection Tool. At that point, the patient will graduate from the study. However, patients and families will be instructed to return to UHWI for follow-up if a complication or recurrence develops. Any delayed complications (e.g., recurrence within 3 months) will be recorded on the patient's Data Collection Tool by the nurse or physician to whom the patient reports it.

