SCLUs are often disabling, scarring, and exquisitely painful. The research literature suggests that both the improvised dressing and the advanced dressing can decrease pain. The advanced dressing has also been shown to decrease scarring. However, children ages 13 - 18 are an especially vulnerable population. They are included in the study because this is the peak age group for SCLU formation, and therefore they are the most likely to benefit if the results can be generalized to them.¹⁵

5. Limitations

Blinding is a challenge inherent to studies of wounds. Although the the healthcare professionals who will monitor and verify wound closure and complications (outcomes) will be blinded, it is not possible to blind the participants or the research team members, because they will provide the wound management in this study.

Despite the incentives to remain in the study (phone cards monthly and wound management supplies at the conclusion of the study), it is possible that there will be a substantial dropout rate, because it is easy for patients with SCLUs to become discouraged, and they may feel that they have derived the major benefits of joining the study after the first few weeks.

All of the published studies of improvised dressings describe wound care performed by health professionals based in urban hospitals or long term care facilities. Although this study will be conducted in a tropical outpatient setting, it too is being conducted by health care professionals in an urban area. Also, Jamaica is significantly more developed than many of the countries for whom the improvised dressing educational program may be beneficial. Therefore, this study may not uniformly generalize to rural areas of tropical developing countries, where health professionals are absent.

6. Acknowledgments:

The researchers would like to thank all participants in the study.

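### The completers-only non-inferiority analysis is not assured to be conservative, because withdrawal depends on outcome, and the plan does not say how area after a switch is handled

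*Combined protocol and SAP*

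**What the plan says.** If superiority over usual practice is not shown, the plan falls back on non-inferiority. Section 3a restricts that analysis: "only those patients completing treatment in the group to which they were randomized will be retained for any non-inferiority analyses". Section 3i repeats it: "80% CIs will be calculated with drop-outs removed from the analyses to evaluate noninferiority". Section 3a's reason is that a per-protocol approach "at worst, would exaggerate the differences between treatment groups, thereby yielding a more conservative estimate".

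Section 3h sets out who leaves. A concern about possible infection, healing-delaying maceration or deterioration leads to an evaluation by an uninvolved physician who is blinded to group. Then: "If the physician determines that the patient's condition has not improved with the prescribed treatments (e.g., antibiotics), the patient will be withdrawn from the study". The same section fixes the later care of everyone who leaves their dressing: a "patient who transitions out of the group to which they were randomized for any reason will receive usual treatment for their ulcer" until the end of the 12 weeks. For groups 2 and 3, that treatment is the control dressing.

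Section 3h also says: "Each patient's data will be recorded for a total of 12 weeks", or until the ulcer has been closed for two weeks. Section 3f plans for losses: "Up to 120 patients will be recruited to allow for a 25% dropout rate". Section 5 says "it is possible that there will be a substantial dropout rate, because it is easy for patients with SCLUs to become discouraged". Superiority uses intent-to-treat with 95% intervals (3i). Sections 3a and 3i both refer to an appendix that is not in the supplied text.

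**The concern.** A per-protocol set is reliably conservative for non-inferiority only if leaving is unrelated to outcome, or related to it in a way that cannot flatter the new treatment. Section 3c makes reduction in ulcer area the outcome for research question 1, and deterioration of the wound is one of the triggers that can end in withdrawal. Patients can therefore be removed because they are doing badly. If more of them are removed from the improvised arm, its completers look better than the arm really is, and the estimate moves towards non-inferiority.

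At stake is the fallback claim. In the supplied text it rests on one analysis set, described as able to err in one direction only. Adding an intent-to-treat analysis is not enough by itself. The plan does not say whether area is still measured after a patient is withdrawn, or how area measured on usual treatment would count.

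**Working it through.** **The plan's own figure.** 90 / (1 - 0.25) = 120, which reproduces section 3f. At full recruitment that is 40 per arm, with 10 per arm allowed to drop out and so be removed from the non-inferiority set.

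**Nominal error.** A two-sided 80% interval leaves (1 - 0.80)/2 = 10% on the side that decides non-inferiority.

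**Inputs.** From the plan: about 30 per arm, the 80% interval, completers only. Assumed, because the supplied text gives no values: SD 50 points of percentage area change; margin 25 points (0.5 SD); true stay-on-dressing difference exactly 25, so non-inferiority is false; withdrawal rates w by arm; and correlation r of 0.3, 0.5 or 0.7 between a withdrawal score and poor final area. The interval is an unadjusted pooled t.

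**Shift in completers.** Removing the fraction w with the worst scores improves an arm's mean by r x SD x k(w), where k(w) = phi(z)/(1 - w) and z is the upper-w normal quantile. This gives k(0.05) = 0.109, k(0.10) = 0.195 and k(0.20) = 0.350.

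**Worked case: 5% usual v 20% improvised, r = 0.5.**
- Bias = 0.5 x 50 x (0.350 - 0.109) = 6.0 points towards the improvised dressing.
- SE is about 50 x sqrt(1/28.5 + 1/24) = 13.85.
- False non-inferiority is about Phi(6.0/13.85 - 1.28) = Phi(-0.85) = 0.20. Simulation with 60,000 trials gives 0.203.

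**Simulated false non-inferiority in completers:**

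| Usual v improvised withdrawal | r = 0.3 | r = 0.5 | r = 0.7 |
|---|---|---|---|
| 5% v 10% | 0.119 | 0.132 | 0.150 |
| 5% v 20% | 0.153 | 0.203 | 0.265 |
| 5% v 5% | 0.099 | 0.099 | 0.099 |
| 20% v 20% | 0.101 | 0.099 | 0.102 |
| 20% v 5% | 0.061 | 0.040 | 0.026 |

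Equal total dropout does not rule this out. With 40 per arm and 25% lost in each, of which 5% v 20% is outcome-related and the rest random, the values are 0.156, 0.211 and 0.281.

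**Requiring both sets, 5% v 20%, same three correlations.**
- Improvised leavers' area taken as observed, having reached the usual-practice mean: 0.148, 0.199, 0.261. Almost nothing is gained.
- As observed, having moved halfway there: 0.127, 0.164, 0.202.
- Leavers scored at the larger of baseline and last pre-switch area, with half the would-be change reached by the switch: 0.091, 0.112, 0.131.

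**The safety definition as a guard.** Section 2 calls the dressing safe if complications are not significantly higher than under usual practice. At 30 per arm, two-sided 5%, power is 24% (Fisher) to 45% (uncorrected chi-square) for complication rates of 5% v 20%, and about 70% to 80% for 10% v 40%.

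**The case against.** **Direction.** A reader might infer that the analysis is biased towards non-inferiority in this trial. The documents do not support that. Section 1b raises infection with plastic bags in the tropics, but the literature review reports no excess of infection or adverse events with plastic wrap, and section 2 expects no serious infections in any group. What stands is that the bias can go either way, whereas section 3a allows only one.

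**There is a rule for switched patients.** For non-inferiority this is correct: section 3a excludes them. The gap concerns area after a switch in any analysis that keeps all randomised patients, including the planned superiority analysis.

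**Blinded evaluation.** The blinded physician limits differential judgement. It does not remove the bias if true failure rates differ by arm.

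**Planned ANCOVA.** Section 3i adjusts for baseline characteristics; the calculation above does not. Under 5% v 20% and r = 0.5, if withdrawal acts through a measured covariate correlated 0.7 with outcome, ANCOVA brings the error from 16% to 10%. If it acts through the outcome itself (covariate correlation 0.5), the change is only from 20% to 18%.

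**The safety definition.** A reader might dismiss it as a guard. That goes too far. Withdrawal follows only unresolved problems, so complications should be at least as frequent as these withdrawals, and the 10% v 40% case shows useful power if half resolve. Section 2 also requires no attributable major adverse events. The guard is partial, and its strength is unknown.

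**Unseen appendix.** It may contain further rules. It could not make the statement in section 3a generally true given section 3h.

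**Conclusion.** The concern holds in this form: the assurance that completers-only analysis is at worst conservative is not justified when section 3h withdraws patients for unresolved wound problems. Under the assumptions shown, false non-inferiority is about 12-15% (5% v 10%) or 15-26% (5% v 20%) when the improvised arm loses more patients for poor outcome, and 3-6% (20% v 5%) when usual practice does. With equal withdrawal it is roughly nominal or conservative in most models; an extreme case with 25% withdrawn per arm purely on outcome gives 15%.

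These figures show direction and possible size only. The supplied text gives no withdrawal rate by arm or cause, no SD and no numeric margin.

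A reader might also conclude either that the superiority result is undermined or that it is untouched. Neither is right. The completers-only bias does not reach the intent-to-treat analysis, but the unstated handling of post-switch area does. The plan should be amended on this point; confidence is medium because the magnitude is assumed and the appendix is unseen.

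**What to change.** Subject to what the cited appendix already contains:

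1. In section 3a, replace the claim of conservatism with a statement that outcome-related withdrawal can bias the per-protocol result in either direction. Report withdrawals by arm and reason.
2. Add an all-randomised non-inferiority analysis and claim non-inferiority only if it holds in both sets. Neither set suffices alone: with the unfavourable scoring in item 4, the all-randomised set alone reaches 17% at 20% v 20% and 19% at 20% v 5% (r = 0.3).
3. Reconcile the two statements in section 3h, 12 weeks of data and withdrawal from the study, so that area and complications are recorded to week 12 after a switch.
4. Name the effect of interest first: staying on the dressing, or as randomised including the switch. Then state how post-switch area enters both the all-randomised non-inferiority analysis and the intent-to-treat superiority analysis. Add a sensitivity analysis that scores section 3h withdrawals as unfavourable. The larger of baseline and last pre-switch area is one option, though debatable. If the as-randomised effect is chosen, as-observed area is the natural main analysis; for the stay-on-dressing effect it protects little.

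**Cost.** SAP wording and continued photographs of leavers; no extra patients. Without withdrawals, power is 74% (arms truly equal, margin 25 points, 30 per arm). Requiring both sets with the unfavourable scoring costs about 2-7 points in most models; at r = 0.5 it goes from 74% to about 71-72% with 5% withdrawn per arm and from 70% to 66% with 20%. If leavers do very badly (averaging a 50-point enlargement, all of it before the switch), it goes from 72% to 65% with 5% withdrawn and from 67% to 52% with 20%. The fix reduces the bias but does not guarantee 10%.
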